## **9.7. Sample Handling**

Blood samples for 3 sets of tests (HbA1c, liver function, and lipid profile) will be taken at the 3 specified visits, with an approximate maximum total volume of 9ml. All blood samples will be taken, handled, analysed and disposed of according to standard NHS procedures and local practice policy. Blood samples will be taken according to the study schedule outlined in appendix B, in order to estimate changes in glycaemic control and other biomarkers. The samples will be sent to NHS laboratories for analysis and results reported to the GP following standard procedures. These data will subsequently be extracted from participants' medical records onto the participant CRF.

## **9.8. Early Discontinuation/Withdrawal of Participants**

Each participant has the right to withdraw from the trial at any time.

During the course of the study a participant may choose to withdraw early from the study treatment at any time. This may happen for several reasons, including but not limited to:

- The occurrence of what the participant perceives as an intolerable AE.
- Inability to comply with study procedures
- Participant decision

Participants may choose to stop treatment and/or study assessments but may remain on study follow-up.

Participants may also withdraw their consent, meaning that they wish to withdraw from the study completely. If a participant decides to withdraw from treatment, we will seek to retain them in the trial for follow-up by explaining the value to the trial of collecting follow up data from all participants by speaking with the participants. However, if the participant wishes to withdraw from follow up we will use their data up to the point that they withdraw unless they request that we do not do so. The reason for withdrawal will be recorded in the electronic case report form (ECRF). Participants that withdraw from the trial will not be replaced. Should a participant wish to withdraw, their information that is held with the provider, will be retained for 10 years following cease of use. This relates to information provided to the intervention provider by the study team and the participant. Cease of use refers to the last login to the online programme by the participant. Each participant can request that their personal information that is retained by the intervention provider is deleted by contacting either the intervention provider or the study team, who will process that request.

In addition, the Investigator may discontinue a participant from the study treatment at any time if the Investigator considers it necessary for any reason including, but not limited to:

- Pregnancy
- Ineligibility (either arising during the study or retrospectively having been overlooked at screening)

- Significant protocol deviation
- Clinical decision

The type of withdrawal and reason for withdrawal will be recorded in the CRF.

### **9.9. Definition of End of Study**

The end of study is the point at which the final data is collected -the last 12 month visit of the last participant.

## **10. SAFETY REPORTING**

### **10.1. Definition of Serious Adverse Events**

A serious adverse event is any untoward medical occurrence that:

- results in death
- is life-threatening (i.e., an event in which the participant was at risk of death at the time of the event; it does not refer to an event which hypothetically might have caused death if it were more severe).
- requires inpatient hospitalisation or prolongation of existing hospitalisation
- results in persistent or significant disability/incapacity
- consists of a congenital anomaly or birth defect.

Other 'important medical events' may also be considered serious if they jeopardise the participant or require an intervention to prevent one of the above consequences.

### **10.2. Reporting Procedures for Serious Adverse Events**

The duration of the SAE recording period for each participant lasts from their enrolment on to the study, to their completion of the study. Any serious adverse event (SAE) occurring to a participant will be recorded at the time that the research team is made aware of the incident, and reported to the REC that gave a favourable opinion of the study where in the opinion of the clinically qualified Chief Investigator the event was 'related' (resulted from administration of any of the research procedures) and 'unexpected' in relation to those procedures. Reports of related and unexpected SAEs will be submitted within 15 working days of the Chief Investigator becoming aware of the event, using the HRA report of serious adverse event form, in accordance with HRA process. We will also proactively ascertain for any additional SAEs at the 3 and 12 month outcome data collection timepoints.

## **11. STATISTICS AND ANALYSIS**

The study results will be reported in accordance with the CONSORT (Consolidated Standards of Reporting Trials) 2010 statements (8). A full analysis plan will be prepared and finalised before any data analysis.

### **11.1. Description of the Statistical Methods**

The primary statistical analysis of efficacy outcomes will be carried out on the basis of intention-to-treat (ITT). This is, after randomisation, participants will be analysed according to their allocated intervention group irrespective of what intervention they actually receive. We will endeavour to obtain full follow-up data on every participant to allow full ITT analysis, but we will inevitably experience the problem of missing data due to withdrawal, loss to follow up, or non-response to questionnaire items.

We will analyse the primary continuous outcome with a linear model adjusting for baseline value of the relevant variable where relevant. For exploratory analyses, we will use analogous models, but interpret the data in an exploratory manner rather than confirmatory. For binary outcomes (e.g. remission), we will test for a difference in proportions, e.g. using Fischer's exact test.

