There is a growing support from observational evidence to suggest that remote support via a digital platform can positively affect the weight and glycaemia of patients with type 2 diabetes who engage with these interventions. One such platform offering remote behavioural and dietary support for people with type 2 diabetes provides a three-month remote behavioural change programme with mentoring from a registered dietitian or nutritionist (health coach), encouraging adoption of a low energy, low-carbohydrate diet, peer group support, structured education articles and activity tracking technology. These elements are accessed via a smartphone or web-based application; each participant additionally receives an instructional handbook, and recipe book (+/-wireless weighing and activity tracking technology). A service evaluation of 190 participants referred as part of routine care from January to July 2018 found that 75% of patients (n=144) started the programme, and 65.3% (94) of these submitted weight readings after 12 months. Of these, 60% achieved over 5% total body weight loss, and 28.7% achieved over 10% body weight loss; the average total 12 month weight change was -7.8kg (+/- 8.6kg). 28.5% of participating patients attended for a blood test with their GP after 12 months as part of routine care; in those with available HbA1c data, there was a statistically significant change in HbA1c compared to baseline (mean -10.4mmol/mol, SD +/- 8.6mmol/mol)(5). An earlier larger cohort of 896 patients who completed a similar programme (3 months of “core” support, plus ongoing access to sustainable advice and encouragement of weekly engagement) over a 1 year period, comprising both self-funded clients and those referred by their GP free of charge, found a significant change in mean weight of -7.12kg (SD 6.37kg) at 6 months and -6.14kg (SD 9.97 kg) at 12 months compared to baseline measures(6). While the weight and glycaemic changes reported appear promising, and clinically significant, these observational studies have several key limitations (including the generalisability of the patient population (a selected group of people with high intrinsic motivation to take part, often in locally limited geographical areas); observational design and lack of a control or comparator group; and significant loss to follow up and absence of follow up data, without the ability to determine why) that preclude drawing reliable conclusions as to the programme’s performance and effectiveness.

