## 6. OBJECTIVES AND OUTCOME MEASURES

Objectives	Outcome Measures	Timepoint(s) of evaluation of this outcome measure (if applicable)

Primary Objective To determine the effectiveness of an app-based programme offering support for a low energy, low carbohydrate diet on glycaemia, compared with usual care in people with type 2 diabetes	Change in participants' HbA1c from baseline to 3 months and baseline to 1 year (co-primary outcomes)	Baseline, 3 months, 1 year
Secondary Objectives 
 
To determine the effect of an app-based programme offering support for a low energy, low carbohydrate diet on remission of type 2 diabetes compared with usual care
 
To determine the effect (Short- and longer-term) of an app-based support programme for dietary change in type 2 diabetes on weight, compared with usual care
 
To determine the effect of an app-based programme offering support for a low energy, low carbohydrate diet on other markers of cardiometabolic risk, compared to usual care
 
To determine the effect on diabetes related distress and quality of life
 
	Number of participants meeting consensus definition for remission from type 2 diabetes at 1 year  Change in participants' weight from baseline to 3 months and baseline to 1 year  Change in participants': - Blood pressure (systolic and diastolic) - Lipid profile (total-, HDL- and LDL- cholesterol, triglycerides) - Liver function (Bilirubin, ALT, ALP, Albumin)  Change in participants' PAID score and EQ5D,	1 year  Baseline, 3 months, 1 year  Baseline, 3 months, 1 year  Baseline, 3 months, 1 year  Baseline, 3 months, 1 year
Process Measures To examine engagement with the programme	Data will be collected on measures of engagement with the three main components of the programme ("Learn", "Track", and "Support"), via the app programme, and change in dietary intake	Baseline, 3 months, 12 months

To examine the demographic profile of participants	patterns (via Intake24 24 hour dietary recall questionnaire) Data (age, gender, ethnicity, level of education, deprivation index, dietary preference) will be collected via questionnaire	Baseline
To explore participants' experience of using the app-based support	Interviews with participants	3 months

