### **11.2. Sample Size Determination**

Based on previous studies of this intervention(5) and studies in similar populations(3), we estimate an 8-10mmol/mol change in HbA1c at 12 months in the intervention group in those who engage with the programme (SD 8.6mmol/mol), with a 1-2mmol/mol (SD 6mmol/mol) change in the control group. With  $\alpha$  and  $\beta$  set at 0.05 this would require approximately 48 participants; however to power for a co-primary outcome would require 72 to 88 participants in total (allowing for variability in estimated effect size). In similar trials of behavioural interventions we would expect retention to follow up of >80%; allowing for the online nature of this trial, and the retention rates of observational studies of this intervention we will aim to recruit 100 participants to allow for cumulative attrition at the intervention sign-up, engagement, and follow up stages.

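### Section 11.1 expects missing data but states no method; by default the 12-month HbA1c analysis would ignore 3-month values, and may be biased either way if drop-out follows early response

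*Combined protocol and SAP*

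**What the plan says.** Section 11.1 commits to intention-to-treat by allocated group. It then concedes that "we will inevitably experience the problem of missing data due to withdrawal, loss to follow up, or non-response to questionnaire items". For the primary outcome it goes on: "We will analyse the primary continuous outcome with a linear model adjusting for baseline value of the relevant variable where relevant". Neither 11.1 nor any other section mentions a repeated-measures model, imputation, a missing-data assumption or a sensitivity analysis.

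Section 6 defines the primary outcome as change in "HbA1c from baseline to 3 months and baseline to 1 year (co-primary outcomes", so HbA1c is measured at both visits as a matter of course.

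Section 11.2 expects more than 80% retention in similar trials, then sets recruitment at 100 "to allow for cumulative attrition at the intervention sign-up, engagement, and follow up stages".

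Section 11 defers detail: "A full analysis plan will be prepared and finalised before any data analysis". That plan is not in the documents.

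**The concern.** A linear model of 12-month HbA1c on arm and baseline can use only participants with a 12-month value. A participant measured at 3 months and then lost contributes nothing to it, although the 3-month result is on file and is probably the best available guide to what the 12-month result would have been.

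The gap matters in this trial for three reasons. App support stops at 3 months, nine months before the second co-primary endpoint. Allocation is open. Of the attrition stages named in 11.2, the first two (sign-up and engagement) concern the app arm mainly, so the reasons for leaving may well differ by arm.

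Two conditions are needed for bias. Drop-out must depend on 3-month response, and 3-month response must predict 12-month HbA1c once baseline and arm are known. If both hold, the benefit is overstated when poor responders leave the app arm. It is understated when good responders leave the app arm or poor responders leave control. Unequal drop-out rates alone do no harm.

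**Working it through.** **Inputs from the documents.** SD of change 8.6 (app) and 6 (control); change of 8-10 in app participants who engage and 1-2 in control; 1:1 allocation of 100 (sections 7 and 11.2). Loss of 20% per arm is the upper end of what 11.2 expects. The pessimistic 35% comes from the section 5 service evaluation, where "65.3% (94) of these submitted weight readings after 12 months" (1 - 0.653 = 0.347). That figure concerns weight readings, so it is only a proxy.

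**Assumptions, not in the documents.** Correlation of 3- and 12-month change 0.6; drop-out log-odds 1 per SD of 3-month change; correlation of baseline with change -0.3 to -0.5. The true difference is taken as 8 - 2 = 6.0 mmol/mol, the cautious end of the 11.2 ranges.

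**The plan's own figure.** Average SD = sqrt((8.6² + 6²)/2) = 7.41. With two-sided alpha 0.05, power 0.95 and a difference of 10 - 2 = 8, n per arm = 2 × 7.41² × (1.960 + 1.645)²/8² = 22.3. That is 46 in total, or 48 with the t distribution, as stated. The SDs are therefore being read as the plan reads them.

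**Standard error.** With 40 per arm retained, sqrt(8.6²/40 + 6²/40) = 1.66. Baseline adjustment at correlation -0.4 multiplies this by sqrt(1 - 0.16) = 0.917, giving about 1.5.

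**Shift by hand, before baseline adjustment.** Let m be the amount by which the mean standardised 3-month change of those retained differs from that of all randomised. Then

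shift = correlation × (SD app × m app - SD control × m control).

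With logistic drop-out of slope 1, m = E[z(1 - p(z))]/(1 - loss), which is 0.173 at 20% loss and 0.292 at 35%.

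- Same mechanism in both arms, 20%/20%: 0.6 × (8.6 - 6) × 0.173 = 0.27. The arms largely cancel; what is left comes from the unequal SDs.
- App arm only, 20%: 0.6 × 8.6 × 0.173 = 0.89.
- App arm only, 35%: 0.6 × 8.6 × 0.292 = 1.51.

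Baseline adjustment removes part of the one-arm shift, because baseline also predicts 3-month change.

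**Baseline-adjusted linear model on available cases, by simulation.** Loss is app/control and the truth is 6.0. Ranges cover baseline-change correlation -0.3 to -0.5. Coverage is of the 95% interval with 50 randomised per arm.

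| Who leaves | Loss | Estimate | Coverage |
|---|---|---|---|
| Random | 35%/20% | 6.0 | 94% |
| Poor responders, both arms | 20%/20% | 6.3 | 94-95% |
| Poor responders, both arms | 35%/20% | 6.7-6.8 | 92% |
| Poor responders, app only | 20%/20% | 6.6-6.8 | 92-93% |
| Good responders, app only | 20%/20% | 5.2-5.4 | - |
| Poor responders, control only | 20%/20% | 5.5-5.7 | - |
| Poor responders, app only | 35%/20% | 7.0-7.3 | 87-88% |
| Good responders, app only | 35%/20% | 4.7-5.0 | 86-87% |

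With correlation 0.4-0.8 and log-odds 0.5-1, the two app-only 35%/20% cases span 6.3-7.9 and 4.2-5.7. With zero correlation there is no bias.

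**Using the 3-month value.** If every drop-out has a 3-month HbA1c, the estimate returns to 5.97-6.03 in these scenarios. In the 7.0-7.3 case it is 6.3-6.5 if half of the drop-outs lack a 3-month value, and 6.9-7.3 if all do, which is almost no correction.

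**The case against.** A reader might infer that the protocol prescribes a complete-case analysis. It does not. Section 11.1 is silent on missing values, a linear model does not exclude imputation or a repeated-measures form, and section 11 promises a full plan before analysis. Complete-case is only the default reading of the one model named. That point stands, and it limits the claim to what these documents leave open.

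A reader might also infer that the 12-month result will be biased, or biased in favour of the app. Neither follows. Both conditions for bias are unverified, the direction depends on who leaves, and similar drop-out in the two arms largely cancels.

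The larger figures need heavy loss, a steep slope and a one-arm mechanism all at once. At 20%/20% with a slope of 0.5 in the app arm only, the shift is 0.3-0.4 and coverage 94%. At 12%/12% (also an assumption) with slope 1, it is about 0.15 with both arms affected and 0.35-0.5 with the app arm only.

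The trial also works to limit loss. There are booked GP visits with reminders and possible use of GP-record values (9.6), and a voucher at 12 months (16.7). For those who stop treatment, "we will seek to retain them in the trial for follow-up" (9.8). The service-evaluation rates in section 5 therefore transfer poorly: one concerns weight readings, and the other, "28.5% of participating patients attended for a blood test with their GP after 12 months as part of routine care", describes routine care rather than scheduled trial visits.

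All of this lowers the likely size. None of it says what happens to the values that are still missing.

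**Conclusion.** The point holds as a should-fix with medium confidence. The documents expect missing data, state no method for it, and by default would set aside a 3-month measurement that the trial already collects. What is established is that the 12-month effect may be biased, in either direction, under two plausible but untested conditions.

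At the upper end of the loss that 11.2 expects, the shift is minor (about 0.3 against a standard error of about 1.5) unless drop-out differs by arm, when it is about 0.6-0.8. Only the pessimistic one-arm case reaches 1.0-1.3, with coverage of about 86-88%. These sizes rest on the assumed correlation and drop-out slope, and on a 6.0 difference whose 8 mmol/mol component 11.2 ties to participants who engage. They illustrate what could happen and are not predictions.

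**What to change.** In 11.1 or the promised analysis plan, before outcome data are seen:

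- Analyse 3- and 12-month HbA1c together in one likelihood-based repeated-measures model with arm, visit, arm-by-visit and baseline-by-visit terms and an unstructured covariance. Alternatively, use multiple imputation by arm that includes baseline and 3-month HbA1c. Read both co-primary contrasts from that analysis, and state that it assumes missing at random.
- Add a delta-adjusted sensitivity analysis over all randomised participants, because the main model cannot correct for those with no 3-month value. Each 1 mmol/mol worse assumed for app-arm drop-outs moves the estimate by 0.35 at 35% loss or 0.20 at 20%. In the worst overstated case (estimate 7.31), a delta of 1.31/0.35 = 3.7 mmol/mol would bring it back to 6.0.

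The cost is some plan wording and slightly more programming, with no new data. Precision hardly changes: the standard error is 1.59 against 1.66 with random 35%/20% loss, and 1.50 against 1.50 with 20%/20% outcome-related loss. The gain is protection against bias, and the main model gives it only for drop-outs who have a 3-month value.

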## 2. LAY SUMMARY

The standard for diabetes management is changing. What was previously thought to be a lifelong progressive condition to be managed primarily with increasing doses of medications, may instead be put into remission (achieving normal or near-normal blood glucose levels without medications) if treated with intensive weight loss support. However, the majority of patients with type 2 diabetes still rely on general dietary advice from primary care professionals. While there is considerable uncertainty regarding the optimal diet composition for people with type 2 diabetes, there is a growing interest from patients, practitioners and the general public in using real-food, low carbohydrate diets to achieve weight loss, improved glycaemic control and even disease remission. A recent small-scale study demonstrated that it was possible, and effective in the short-term, for practice nurses in primary care to support patients with type 2 diabetes to adopt a real-food, low-carbohydrate weight loss diet. However the patients and healthcare professionals who took part in this study were keen to know whether digital interventions and app-based

support could be an alternative way to achieve the same results, with the potential for more frequent support without increasing the demand on the primary care workforce. This study aims to investigate whether an app-based low-carbohydrate intervention with remote behavioural support is effective at improving glycaemia, weight, and other markers of cardiometabolic risk, for people with type 2 diabetes in primary care.

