## 7. STUDY DESIGN

This is an individually randomised controlled trial. Participants, recruited via GP practices, will be randomised 1:1 with simple randomisation and no stratification to either the intervention group or control (usual care). They will be enrolled in the study for 1 year, of which the intervention (dietary support via the app) will run for 3 months. Most study procedures will be conducted online or remotely (by telephone) including: screening, eligibility assessment, informed consent, randomisation, engagement with the app-based intervention. Participants will be asked to attend 3 face to face appointments for the research study at their local GP practice for measurements to be taken (weight, blood pressure) and blood tests, at baseline, 3 months and 1 year, and will have 1 additional telephone contact with their GP or practice nurse before starting the intervention. Face to face appointments will be incorporated with routine clinical appointments when possible.

A flow diagram showing the trial design is given in Appendix A

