### **1. Online:**

Participants will be asked to complete a baseline questionnaire requesting demographic information and their current medication, and the standard questionnaires that will be used in the study (the Problem Areas in Diabetes (PAID) score, the EQ5D (quality of life assessment), and a 24 hour dietary recall questionnaire (“Intake24 dietary assessment tool”, where participants are asked to record all food and drink intake in the last 24 hours). This will also further assess whether people are sufficiently able to complete online trial procedures, and only those who complete the questionnaire will be randomised. Participants will be informed in the Participant Information Sheet that they will only be able to enter the study after completing each individual questionnaire fully in one attempt as the system will not allow them to go back into each

questionnaire to answer the remaining questions later. Overall there are 3 questionnaires for each participant to complete. These should take less than 30 minutes to complete. Patients will be able to fill in the baseline questionnaires and 24 hour dietary recall at any time after completion of the online consent form but before the appointment at their GP practice, as long as they complete each questionnaire in one attempt. Should a participant not complete their questionnaires, reminder emails will be sent at one and two weeks after they received the initial invite to complete the questionnaires.

2. At the GP practice (visit 1)

Having completed the online assessment, participants will be asked (via message on their screen on completing the assessment, and followed up via email) to book the in-person portions of their baseline assessment at their GP practice for measures which cannot be conducted online. At this appointment (with a nurse or healthcare assistant), their height, weight and blood pressure will be measured and recorded, and a blood sample taken for baseline values (HbA1c, lipid profile, liver function tests). Once their practice confirms they have attended this appointment they will be sent a link to the randomisation system.

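### Remission is compared without adjustment for baseline HbA1c, which is measured before an unstratified randomisation; the test is valid but gives up some precision that costs almost nothing to recover

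*Combined protocol and SAP*

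**What the plan says.** Section 6 lists remission first among the secondary outcomes: "Number of participants meeting consensus definition for remission from type 2 diabetes at 1 year". No HbA1c threshold is printed. The lay summary (section 2) describes remission as "achieving normal or near-normal blood glucose levels without medications", so it has a glycaemic condition and a medication condition.

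Section 11.1 analyses the primary continuous outcome "with a linear model adjusting for baseline value of the relevant variable where relevant". For remission it says "For binary outcomes (e.g. remission), we will test for a difference in proportions", gives Fisher's exact test as an example, and names no covariate. Section 11.3 reports differences in proportions or means with 95% confidence intervals and tests at 5% two-sided.

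Under section 9.3, HbA1c is drawn at visit 1, and the randomisation link goes out only once the practice confirms attendance. Section 7 has participants "randomised 1:1 with simple randomisation and no stratification". Section 11 promises a full analysis plan before any analysis. Nothing in the document adjusts remission for baseline HbA1c.

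**The concern.** Someone who starts just above the remission threshold needs a small fall in HbA1c to cross it, and someone who starts far above needs a large one. Baseline HbA1c therefore carries much of the information about who meets the glycaemic condition. It is a genuine pre-randomisation covariate, collected at the visit every participant must attend before being randomised. Leaving it out treats predictable variation as noise.

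Simple randomisation of 100 people does nothing to even out baseline HbA1c. If one arm happens to start lower, the plan corrects the HbA1c comparison for this but not the remission comparison. The two glycaemic results could then drift apart for reasons unrelated to the programme.

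What is at stake is the precision of a secondary outcome, and how far its estimate depends on the imbalance that happens to occur.

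**Working it through.** **The plan's own figure.** The document gives no power, rate or sample size for remission. Section 11.2 sizes the trial on HbA1c only. Its figure of about 48 reproduces:

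- Pooled SD = √((8.6² + 6²)/2) = 7.41.
- With a difference of 8, two-sided alpha 0.05 and power 0.95, the total is 46 by the normal approximation and 48 by the noncentral t.

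So the section 11.2 inputs are being read as intended.

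**How strongly baseline predicts the glycaemic part.** Suppose a person starts d mmol/mol above the threshold and the change does not depend on baseline. The chance of ending below the threshold is Φ((Δ − d)/SD), where Δ is the mean fall. Using the section 11.2 midpoints:

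| d | Intervention (Δ = 9, SD 8.6) | Control (Δ = 1.5, SD 6) |
|---|---|---|
| 5 | Φ(0.47) = 68% | Φ(−0.58) = 28% |
| 15 | Φ(−0.70) = 24% | Φ(−2.25) = 1% |
| 25 | Φ(−1.86) = 3% | Φ(−3.92) < 0.1% |

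This needs no assumed threshold. It concerns the glycaemic condition only.

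**Simulation inputs.**

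- *From the document:* 40 analysed per arm (100 × 0.80 = 80, taking the retention expectation in section 11.2 at its floor). Falls of 8 (SD 8.6) against 1.5 (SD 6), which lie within the section 11.2 ranges.
- *Assumed, not in the document:* threshold 48 mmol/mol; baseline mean 55-60 and SD 8-12, with people already below the threshold excluded; 50-70% off medication in both arms.

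**Comparison.** The unadjusted difference in proportions is set against a standardised risk difference. The latter fits a penalised logistic model on arm and baseline HbA1c, then averages predicted risk under each arm over everyone: (1/N) Σ [p̂(1, xᵢ) − p̂(0, xᵢ)].

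| Remission decided by | Variance cut | Power gain | Shift in unadjusted difference per 1-SD imbalance | Shift after adjustment |
|---|---|---|---|---|
| HbA1c and being off medication | about 3-14% | roughly 1-8 points | about 2-3 percentage points | close to zero |
| HbA1c alone (upper bound) | about 20-26% | 10-15 points | about 4 percentage points | close to zero |

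A variance cut v is worth 1/(1 − v) in sample size. For the first row that is 1/0.97 = 1.03 to 1/0.86 = 1.16, or about 3-16% more participants.

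**Sensitivity.**

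- A separate simulation used a fall of 9, baseline means 7, 12 and 17 above the threshold, and 60% against 40% off medication. Adjustment gained 4-9 points over an unadjusted chi-square, with a variance cut of 8-9%. Its adjusted test was slightly liberal (about 6%), which flatters the gain a little.
- When people who start higher also fall further (slope 0.3), with 60% off medication, the gain was 3-5 points. It shrank but did not vanish.

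**Validity.** Under no effect, type I error was 3.0% for Fisher's exact test, about 5% for the unadjusted chi-square, and about 5-6% for the adjusted analyses. The gains above are measured against unadjusted score or chi-square tests, so they do not borrow from Fisher's conservatism.

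**The case against.** The strongest reply is that nothing here is invalid. The planned test holds its size, the estimate is unbiased on average, and chance imbalance is already part of its standard error. With remission of 37% against 15% at 40 per arm, for example, that standard error is √(0.37 × 0.63/40 + 0.15 × 0.85/40) = 0.095, or 9.5 percentage points. A shift of 2-3 points sits well inside it. Remission is secondary and the trial claims no power for it. With few events a simple test is a defensible choice, and plain logistic regression can break down: separation occurred in up to 37% of runs in the rarest-event scenario. All of this stands, and it limits the point to a modest one.

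Two further replies carry less weight. The words introducing Fisher's test as an example leave open which test of a difference in proportions is used, not whether to adjust. The provision in section 11.1 for analogous models concerns exploratory analyses, and the next sentence treats binary outcomes separately. The promised full analysis plan could add the covariate, but that makes it the place for the change rather than a reason to leave it out.

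A reader might infer a much larger loss. Drawing baseline HbA1c from an untruncated normal distribution and letting HbA1c alone decide gives power rising from 0.61 to 0.79, or from 0.39 to 0.66, and variance cuts of up to 46%. The document does not support those figures. Section 8.2 requires current diabetes, not in remission. Those settings put Φ((48 − 60)/8) = 7% to Φ((48 − 55)/12) = 28% of participants below the threshold at entry, where they would already count as remitted. The lay summary's medication condition also rules out HbA1c alone as the working case. People below 48 but on medication could be eligible, so excluding all of them is itself an assumption. Keeping them in, with the medication condition applied, gives gains of about 3-10 points, which is little different.

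**Conclusion.** The point holds as a matter of precision. Section 11.1 leaves out of the remission analysis a strong, already-collected, pre-randomisation predictor that the design does not balance. Under the stated assumptions the cost is about 3-14% of variance and roughly 1-8 power points. The bound of about 20-26% and 10-15 points applies only if medication status played no part. The threshold, baseline distribution and off-medication shares are not in the document, so these are ranges and not forecasts.

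A reader might go further and call the planned comparison biased, or say that imbalance would create remissions whatever the programme does. The plan does not support that. Randomisation makes the unadjusted comparison fair on average, and only its dependence on the imbalance that actually occurs is at issue. No claim the trial makes about its primary outcome is affected. This is a cheap improvement.

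**What to change.** In section 11.1, or in the full analysis plan that section 11 promises, state the following before outcome data are seen. Timing matters because section 9.4 leaves the study team unblinded.

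- Remission at 1 year is analysed with a logistic model on arm and continuous baseline HbA1c, fitted by penalised likelihood if remissions are few.
- The main result is the standardised risk difference with a robust 95% CI, which keeps the reporting scale of section 11.3.
- The unadjusted difference in proportions, or Fisher's exact test, is reported as the supportive analysis.

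The cost is one or two sentences, with no new data and no added burden on participants. The downside is a model-based estimate that needs a penalised fit when events are sparse, with simulated type I error of about 5-6%.
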